3.3.4.9. Withdrawal and Lost to follow-up

Patients may be withdrawn from the study for a number of reasons. The following is a summary of the possible reasons for withdrawal:

- Subjects may voluntarily withdraw from the study. The reason for withdrawal must be documented on the Termination CRF
- After the implant procedure, some subjects may not return for follow-up visits. A minimum of three (3) attempts to contact such patients must be made. All attempts are to be documented on the Termination CRF.

In some cases, an implant procedure will be initiated (i.e., an attempt to pass or deploy the device) but is aborted prior to device deployment. Such patients maintain their enrollment status (since this is an intent-to-treat study), but need not be followed. On the other hand, if a patient is initially screened and enrolled, but no procedure is ever initiated, the patient is cancelled and his/her enrollment position is made available to another patient.

Patients who are enrolled in the study group and are converted to surgery due to peri- or post-implantation complications will be followed for a minimum of 12 months after the conversion to open repair. Conversion to surgery is documented on the Procedure CRF.

3.3.4.10 Final assessment

Patients who have completed 60 months of follow-up will continue annual follow-up examinations for life as their physician's standard of care. These follow-up visits will include a physical examination, a CT, and a plain film x-ray as defined in the Chart of Study Procedures. Subjects who received a Medtronic Thoracic Stent Graft System implant and who choose to discontinue participation in the study prior to study completion will be contacted to perform a final assessment prior to study closure. The final assessment will be recorded on Post-Operative Assessment and Termination CRFs.

A Termination Case Report Form will be completed for every subject regardless of the reason for study termination.

A chart may be found in Table 1 on page 24 indicating the times at which procedures and tests will be performed.

3.3.5. Scientific Soundness and Analysis of Data

All patients will be treated using the same inclusion/exclusion criteria and are treated under the same protocol. Standard data forms will be used to collect information about all procedures and evaluations performed, to provide comprehensive documentation of the study. Each patient will be carefully monitored following treatment at specified intervals for evaluation of adverse effects and clinical effectiveness of the device.

3.3.5.1 Description of Endpoints

Primary endpoints will be early (at 30-days) and late death (at one-, two- and five-years), re-interventions, and surgical conversion (early or late), as well as any post-procedural stroke (early or late), ischemic or hemorrhagic events causing motoric, language or cognitive compromise.

Secondary endpoints will include access vessel complications (including dissection, thrombosis, embolization), myocardial infarction, renal failure, sepsis, pulmonary failure, blood loss over 1000cc, stent graft migration, endoleaks, technical observation (including twisting, kinking, or fracture), loss of stent graft patency (occlusion), aortic valve function (AI>2+), and any malperfusion to aortic branch-vessels (diagnosed with CTA or clinical diagnosis).

3.3.5.3. Analysis of Endpoints

Data Analysis Sets

The primary endpoint analysis set will include all enrolled subjects who had at least one study stent graft implanted.

The Intent-to-Treat (ITT) analysis set will include all enrolled subjects who had an infra-arterial access procedure with intent to receive the study device. The primary endpoint will be reported for this analysis set as well.

Analysis of the Primary Endpoint

The primary endpoint will be analyzed using the exact binomial test method. The null hypothesis will be rejected if the upper limit of the one-sided 95% confidence interval on the 30 days mortality rate is less than 25%. The one-sided upper 95% confidence interval on the 30 days mortality rate will be calculated using the exact binomial test method.

The remainder of the primary endpoint will be presented and analyzed descriptively by reporting, for categorical variables, the number of known values and the percentage in each category, and for continuous variables, the number of known values, the mean, standard deviation (SD), median and the minimum and maximum number of subjects.

Analysis of the Secondary Observations

All secondary endpoints will be presented descriptively by reporting, for categorical variables the number of known values and the percentage in each category, and for continuous variables the number of known values, mean, standard deviation (SD), median, minimum and maximum of subjects meeting the endpoint.

Analysis of Baseline Variables

Baseline variables will be presented descriptively as described in the section above.

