3.3.3. Study Design

This early feasibility study is a prospective evaluation of patients receiving the device to determine the proportion in whom successful implantation is achieved, as indicated by exclusion of the thoracic lesion and graft patency at implant, time of discharge, and 1, 6, and 12 months, and annual visits through 5 years following implantation, and to determine the proportion of patients who die or experience adverse events during and after the implantation. Furthermore, the percentage of patients in whom technical and clinical success is achieved, will be determined. Additional endpoints include length of stay in intensive care unit following the procedure, and total length of hospital stay.

Twenty patients will be enrolled in this feasibility study. The enrollment will be performed in five-patient increments, and the results of each five-patient group will be analyzed and reported prior to enrolling further patients. This modus operandi serves as risk mitigating strategy.

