3.3.4. Study Procedures

3.3.4.1 Patient Screening and Enrollment

Investigators will assess potential subjects diagnosed with Type A thoracic aortic dissection, retrograde Type A thoracic aortic dissection of the ascending thoracic aorta for their suitability for enrollment in the clinical study. If the patient appears to meet the eligibility criteria, the investigator will discuss the study with the patient and provide information relating to the potential risks and benefits, and required follow-up procedures per the informed consent process. After the patient has voluntarily signed and dated the informed consent document, the patient will be considered a study candidate. If a patient does not sign the informed consent document, then no further procedures for the clinical study will occur. Subjects who were considered for the study but do not qualify for enrollment will be documented as ineligible on the Subject Screening Log. Subjects enrolled, but with no device implant will be followed through the one-month follow-up only.

Those subjects who sign and date the informed consent document, or who have their Legally Authorized Representative sign and date the informed consent document, and meet all of the study eligibility criteria will be eligible for enrollment into the clinical study. The subject will be considered enrolled at the time the Medtronic Thoracic Stent Graft System is introduced into the arterial access vessels.

Documentation of the following will be obtained prior to the implant procedure:

- Informed consent
- Demographic data
- Medical history
- Vital signs [heart rate, blood pressure, respiratory status, pulse evaluation
(Left and right Radial, Dorsalis, and/or Tibial artery)]
- Pregnancy test (females of child bearing potential)
- Clinical laboratory tests: serum creatinine
- CT of the Chest/Abdomen/Pelvis with and without contrast; MRA, may be used at the investigator's discretion.
- Echocardiogram

All subjects will undergo a neurological examination when possible depending upon the urgency of the procedure and patient availability.

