3.3.4.2. Implant Procedures/Treatment

All investigators will read, understand and be trained to the Medtronic Thoracic Stent Graft System Instructions for Use (IFU) (please see Appendix 14) prior to initiation of the procedure.

The principles of endovascular repair of the type A dissections is very similar to the approach to the type B aortic dissection. The route of access is either through the iliofemoral vessels, the brachiocephalic vessels, or a transapical approach via a small left thoracotomy. Through and through true-lumen access with the guidewire is confirmed using the intravascular ultrasound (IVUS) and anatomic information obtained by pre-procedural computer tomography angiogram (CTA). The size of the stent graft is selected based on the CTA and the IVUS- interrogation. The stent graft will then be delivered and deployed in the ascending aorta using a stiff guidewire. An aortic angiogram is performed to delineate the location of the coronary arteries and the innominate artery as they relate to the true and false lumen. A dissection occurs when a tear of the intima (the inner lining) allows blood to leak into the media (middle layer). This creates two passages for blood: a true lumen, which is the normal passageway of blood, and a false lumen, the newly created passageway. The cardiac cycle will be transiently halted by administration of intravenous adenosine or rapid ventricular pacing. Both methods are well established for effectively reducing the impulsive force of the cardiac output by temporarily halting the heart rate or reducing left ventricular filling, respectively. These methods allow for controlled and precise placement of the stent graft in the desired location of interest.

The usual and customary monitoring associated with procedures for the ascending aorta and arch will be utilized. These include but are not limited to multiple invasive arterial monitoring (at

least 1 radial and 1 femoral line), Cerebral oximetry, Massimo 4 channel continuous EEG monitoring, internal jugular or subclavian venous access to allow for swan-ganz catheter.

The following events will be documented in the medical records and in the CRFs as applicable:

- General, regional, or local anesthesia will be employed during the endovascular procedure per Investigator's discretion. The method of anesthesia will be documented.
- Antibiotics will be administered per Investigator's standard regimen.

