- Arterial site will be accessed per Investigator's standard method.
- Systemic heparin will be administered per the Institution's standard regimen at any time during the procedure.
- Verification of dimensions and characterization of the dissection and pertinent arteries will be conducted with an angiogram at the time of the procedure and prior to the insertion of the Medtronic Thoracic Stent Graft System. The Investigator will verify dimensions and characterizations of the subject's anatomy in relation to the Medtronic Thoracic Stent Graft System. Subjects who are found not to be candidates for Medtronic Thoracic Stent Graft System, because of findings detected during the treatment angiogram, will be documented as screen failures on the Screening Log.
- All Medtronic Thoracic Stent Graft System used for implantation and any issues related to the Medtronic Thoracic Stent Graft System will be documented in the medical chart and on the CRFs.
- Fluoroscopic guidance will be used for placement of the stent graft throughout the endovascular procedure. Total fluoroscopic time and the amount of contrast media used will be documented on the operative notes.
- Devices should be deployed following all the steps in the IFU.
- At the discretion of the Investigator, Intravascular Ultrasound (IVUS) may be used in conjunction with procedural angiography to verify the position of the proximal entry tear or luminal characteristics and to optimize implantation of the device. Additional procedures performed during the treatment will be documented on the appropriate CRFs.
- Upon completion of the procedure, a final run-off angiography will be performed to document the status of the Medtronic Thoracic Stent Graft System, the coverage of the proximal entry tear and the surrounding vasculature.
- The estimated volume of blood replaced, any technical observations and adverse events experienced during the treatment will be documented.
- The cut-down site, if necessary, will be closed as per standard of care.

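### The 25% mortality test is assigned to implanted patients and the intent-to-treat set has no stated decision role, so one death before implant can turn a fail into a pass

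*Combined protocol and SAP*

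**What the plan says.** **Analysis sets (3.3.5.3, and Analytical Sets in the 3.1 synopsis).** "The primary endpoint analysis set will include all enrolled subjects who had at least one study stent graft implanted". Separately: "The Intent-to-Treat (ITT) analysis set will include all enrolled subjects who had an infra-arterial access procedure with intent to receive the study device". (The synopsis has intra-arterial; the difference looks like a text-reading slip and nothing rests on it.) On the role of ITT, 3.3.5.3 says only: "The primary endpoint will be reported for this analysis set as well".

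**Decision rule (3.3.5.3).** The null hypothesis is rejected if the "upper limit of the one-sided 95% confidence interval on the 30 days mortality rate is less than 25" per cent, by the exact binomial method. The rest of the primary endpoint is descriptive.

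**Enrolment (3.3.4.1).** "The subject will be considered enrolled at the time the Medtronic Thoracic Stent Graft System is introduced into the arterial access vessels". Both analysis sets require enrolment.

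**Before enrolment (3.3.4.2).** Patients found not to be candidates "because of findings detected during the treatment angiogram, will be documented as screen failures on the Screening Log". The permitted routes are iliofemoral, brachiocephalic, "or a transapical approach via a small left thoracotomy".

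**Follow-up without an implant.** There are three statements. Section 3.3.4.1 follows enrolled patients with no implant to one month only. Section 3.3.4.8 (Conversion to Surgery) follows converted or observed patients exactly as the others. Section 3.3.4.9 says that a patient whose procedure is aborted before deployment stays enrolled, because this is an intent-to-treat study, but does not have to be followed. The same section cancels and refills the place of a patient who is enrolled but has no procedure started.

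**The concern.** Implantation happens after enrolment and is part of what the study examines. A test restricted to implanted patients answers a conditional question: mortality among those in whom delivery worked. The documents expect delivery to fail at times. Sections 3.3.4.8 and 3.3.4.9 provide for incomplete implantation and aborted procedures, and vessel rupture and cardiac perforation are listed as possible serious complications. A death in that window is absent from the set that carries the test. So are a stroke or a surgical conversion without an implant, which are also primary endpoint components (3.3.5.1).

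The plan defines a set that would count these patients but gives it no part in the decision, although 3.3.4.9 describes the study as intent-to-treat. With 20 patients the rule turns on a single death, so the choice of set is not a detail. The conflicting follow-up statements could also leave 30-day status unknown for exactly the patients who separate the two sets.

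**Working it through.** **Inputs.** 20 enrolled (3.1, 3.3.3); exact binomial method, one-sided 95% upper limit, 25% margin (3.3.5.3). The documents give no expected mortality, power, critical number of deaths or pre-implant death rate, so there is no figure to reproduce. What follows is what the stated rule implies.

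**Step 1: the rule in deaths.** For x deaths in n patients the upper limit U solves

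Σ(k=0..x) C(n,k) U^k (1−U)^(n−k) = 0.05.

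| Deaths/n | Upper limit | Result |
|---|---|---|
| 0/20 | 13.91% | pass |
| 1/20 | 21.61% | pass |
| 2/20 | 28.26% | fail |
| 3/20 | 34.37% | fail |
| 1/19 | 22.64% | pass |
| 1/18 | 23.77% | pass |
| 1/17 | 25.01% | fail |

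With 20 patients the rule allows at most one death. Its true size at 25% mortality is 0.75^20 + 20 × 0.25 × 0.75^19 = 2.4%.

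**Step 2: deaths after device introduction but before implant.**
- Two deaths, one before implant: implanted set 1/19, 22.64%, pass; ITT 2/20, 28.26%, fail.
- Three deaths, two before implant: implanted set 1/18, 23.77%, pass; ITT 3/20, 34.37%, fail.

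**Step 3: a death after access but before device introduction.** This patient is not enrolled and is in neither set. If 20 others are enrolled and implanted and one dies, both sets show 1/20 (21.61%, pass). Counting the accessed patient gives 2/21 (27.06%, fail).

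**Step 4: chance of a false pass.** Assume that true 30-day mortality from device introduction is 25%, of which q occurs before implant, and that these deaths are the only non-implanted patients. With k pre-implant deaths, 20 − k patients are tested. The rule then allows one death if n is 18 to 20, none if n is 11 to 17, and cannot be met if n is 10 or fewer. Summing over k, with post-implant death probability 0.25 − q and survival 0.75:

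P(pass) = Σk C(20,k) q^k × P(implanted patients meet the rule).

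For q = 5 points:
- k = 0: 0.75^20 + 20 × 0.20 × 0.75^19 = 2.0%
- k = 1: 20 × 0.05 × (0.75^19 + 19 × 0.20 × 0.75^18) = 2.6%
- k = 2: 190 × 0.05² × (0.75^18 + 18 × 0.20 × 0.75^17) = 1.6%
- k ≥ 3: 0.1%

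The total is 6.3%. Over a range of q:

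| Pre-implant share of the 25% | Chance of passing, implanted set | Chance of passing, all deaths counted |
|---|---|---|
| 0 points | 2.4% | 2.4% |
| 2.5 points | 4.1% | 2.4% |
| 5 points | 6.3% | 2.4% |
| 10 points | 12.2% | 2.4% |

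**Step 5: the other direction.** Suppose one of 20 enrolled patients dies after implant and three are not implanted but survive. ITT gives 1/20 (21.61%, pass) and the implanted set 1/17 (25.01%, fail). The result depends on who is excluded, not only on how many die.

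**The case against.** The best defence is that nothing is hidden. Section 3.3.5.3 reports the primary endpoint for ITT as well, so in the two-death example 2/20 would stand beside 1/19. Results are reported after every five patients, serious events go to FDA within five working days, and a DSMB oversees the study. Two of the small series cited in 2.1.1, of 15 and 10 patients, report technical success or deployment in every case, so pre-implant deaths may be rare. This is a 20-patient early feasibility study.

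That stands as to visibility among enrolled patients. It does not settle which result decides the test when the two sets disagree, and it does not reach deaths before device introduction.

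A reader might infer more than the text supports:
- **That ITT is left empty.** The enrolment trigger only truncates it. Patients with the device introduced but not implanted stay in ITT, and 3.3.4.9 confirms their status.
- **That the 25% rule is barred from ITT.** The plan is silent on this.
- **That patients harmed at access or angiography are logged as screen failures.** Section 3.3.4.2 says this only of patients found unsuitable on the angiogram.
- **That transapical patients are excluded by design.** The enrolment wording does not fit that route, but 3.3.4.2 also specifies arterial lines and an aortic angiogram. Read literally, the wording would also leave successfully implanted transapical patients unenrolled. This is a drafting problem.
- **That implantation success or access complications cannot be estimated.** The aim in 3.3.3, "to determine the proportion in whom successful implantation is achieved", is not part of the primary endpoint, and access complications are secondary. Neither is tied to the implanted set.

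**Conclusion.** The point holds for the decision rule. As written, the 25% test belongs to implanted patients, ITT has no stated role in the decision, and one death between device introduction and implant is enough to turn 2/20 (fail) into 1/19 (pass). The exact limits rest only on figures in the plan.

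The false-pass rates rest on an assumed pre-implant share of mortality. At 2.5 points the rate (4.1%) stays within the nominal 5%; at 5 and 10 points it does not (6.3% and 12.2%).

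It would go too far to say that the choice of set always favours the device. Leaving out deaths does; leaving out non-implanted survivors works against it. Deaths after access but before device introduction are a smaller, separate gap: they are in neither set.

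**What to change.** 1. In 3.3.5.3 and in the 3.1 synopsis, name ITT as the decision set for the exact 25% test and report the implanted set as supportive.
2. List all deaths and major events between the start of vascular or apical access and device introduction, so that patients outside both sets are visible.
3. Word the enrolment definition (3.3.4.1) and the ITT definition (3.3.5.3) so that they cover the transapical route allowed in 3.3.4.2.
4. Reconcile 3.3.4.1, 3.3.4.8 and 3.3.4.9 on follow-up of patients without an implant. The test needs 30-day vital status for every ITT patient; without it, moving the test to ITT does not work.
5. Reconcile the cancelled-enrolment wording in 3.3.4.9 with 3.3.4.1, under which nobody is enrolled before the device is introduced.

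The cost is protocol and analysis wording. Section 3.3.4.1 already provides one-month follow-up for enrolled patients with no implant. The reported mortality may be slightly less favourable.

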3.1 Investigational Plan Synopsis

Study Title:	Proposed Single Center Investigational Device Exemption: Feasibility of Endovascular Repair of Ascending Aortic Dissections
Investigational Device:	Medtronic Thoracic Stent Graft System
Sponsor:	The Heart Hospital Baylor Plano Baylor Scott and White Research Institute
Principal Investigator and Co Investigators:	PI: [name] Sub-I: [name]; [name]; [name], [name] and J. [name]
Investigational Site:	The Heart Hospital Baylor Plano [name] [name]
Study Purpose:	The purpose of this early feasibility study is to investigate the outcome of selected patients with ascending thoracic aortic pathologies including type A aortic dissection, who are suitable for endovascular repair with the Medtronic Thoracic Stent Graft System
Number of Subjects:	20
Study Type and Duration:	Prospective, Single Center, Non-randomized, Single arm study. The Duration of the investigation is anticipated as follows: 
• Time to Complete Enrollment: 5 Years• Subject follow up time: 5 years from last subject enrollment

Intended Use:	
 • The Medtronic Thoracic Stent Graft System is intended for endovascular repair of the Type A Thoracic Aortic Dissection, Retrograde Type A Thoracic Aortic Dissection of the Ascending Thoracic Aorta (with no involvement of the Aortic Valve) • Location of treatment will be the area between the Sinus of Valsalva and the innominate artery orifice. • High risk subjects having appropriate anatomy will be enrolled in the study. • Anatomic Limitations: 
 ○ The proximal landing zone will allow placement of the stent graft as to not inhibit valvular function, occlude a coronary ostium or proximal bypass graft; ○ Distal landing zone must allow for continued perfusion of critical cerebral vessels; ○ Ascending aorta between 28-44 mm in diameter

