3.2.3. Duration of the investigation

Accrual of study subjects will occur over approximately 5 years with all subjects to be followed at 1 month, 6 month, and 12 month intervals post-procedure followed by annual follow-up through 5 years post implant. Per standard of care, the patients will undergo lifelong follow-up after they have completed the study.

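### Late primary endpoints are reported as a percentage of known values, with no censoring rule, no competing-risk rule and no interval, so the late rates can be biased, in a direction the plan leaves open

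*Combined protocol and SAP*

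**What the plan says.** Section 3.3.5.1 defines the primary endpoint broadly: "Primary endpoints will be early (at 30-days) and late death (at one-, two- and five-years), re-interventions, and surgical conversion (early or late"), and it adds post-procedural stroke, early or late.

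Section 3.3.5.3 gives a formal method for one component only, with a threshold of 25%: "The null hypothesis will be rejected if the upper limit of the one-sided 95% confidence interval on the 30 days mortality rate is less than" that value. For the rest of the primary endpoint the categorical summary is "for categorical variables, the number of known values and the percentage in each category". No Kaplan-Meier estimate, censoring rule, competing-risk method, missing-data rule or confidence interval is given for these components. The main analysis set is implanted subjects ("The primary endpoint analysis set will include all enrolled subjects who had at least one study stent graft implanted"), and the primary endpoint is also reported for the ITT set.

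Follow-up is not complete for everyone:

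- **Lost subjects.** Section 3.3.4.9 expects some ("After the implant procedure, some subjects may not return for follow-up visits"). It requires three contact attempts and describes no search for vital status.
- **Enrolled, no implant.** Section 3.3.4.1 follows them to one month only.
- **Aborted before deployment.** Section 3.3.4.9 keeps them enrolled under intent to treat but does not require follow-up.
- **Converted to surgery.** Section 3.3.4.9 sets a minimum of 12 months. Section 3.3.4.8 (Conversion to Surgery) says that converted or observed subjects are followed exactly like the others, then names forms at 1, 6 and 12 months.

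On timing, "Accrual of study subjects will occur over approximately 5 years". Sections 3.3.3 and 7 have each group of five analysed and reported before more are enrolled. The Synopsis gives "Subject follow up time: 5 years from last subject enrollment".

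**The concern.** Late death, stroke, re-intervention and conversion are events in time, observed over unequal and sometimes truncated follow-up. A percentage of known values at a landmark handles this badly. A subject who dies in month 3 is known at 5 years. A subject last seen alive in year 3 is not, and drops out of the denominator along with three years of event-free observation. The percentage then depends on who was lost as well as on how many died.

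For the non-fatal events there is a second gap. The plan does not say whether a subject who dies without a stroke counts as a known stroke-free value or as unknown, and the two readings give different denominators.

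Most of the primary endpoint rests on these summaries. With 20 subjects, a few of unknown status move a rate by several points, and a bare percentage does not show that. Results are also reported group by group as a risk-mitigation step, so a distorted late rate could reach those judging whether to continue.

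**Working it through.** The documents give no late event rate, loss rate or sample-size derivation for these components, so there is no plan figure to reproduce.

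**Inputs**
- n = 20: "Twenty patients will be enrolled in this feasibility study" (section 3.3.3).
- Illustrative survival S of 86%, 80% and 75% at 30 days, 1 year and 5 years, from the 22-patient ascending endovascular series in section 2.1.1.
- Assumption: loss hazard c of 0.05 or 0.10 per year. The documents give no figure.
- Reading adopted: percentage = deaths observed by T / (deaths observed by T + subjects known alive at T).

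**1. Loss unrelated to prognosis, 5 years**

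Piecewise-constant death hazards per year:
- 0 to 30 days: ln(1/0.86)/(30/365.25) = 1.836
- 30 days to 1 year: ln(0.86/0.80)/(1 − 0.0821) = 0.0788
- 1 to 5 years: ln(0.80/0.75)/4 = 0.0161

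Observed deaths in an interval (a, b) are S(a)·e^(−ca)·h/(h+c)·[1 − e^(−(h+c)(b−a))]. Subjects known alive at 5 years are 0.75·e^(−5c).

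| c per year | Observed deaths | Known alive | Known-values percentage | True |
|---|---|---|---|---|
| 0 | 0.25 | 0.75 | 25.0% | 25% |
| 0.05 | 0.1397 + 0.0584 + 0.0432 = 0.2413 | 0.5841 | 0.2413/0.8254 = 29.2% | 25% |
| 0.10 | 0.1394 + 0.0569 + 0.0374 = 0.2337 | 0.4549 | 0.2337/0.6886 = 33.9% | 25% |

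The excess is 4.2 or 8.9 points, about 0.8 or 1.8 patients in 20. Kaplan-Meier targets 25% here because loss is independent of death.

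**2. Loss related to prognosis**

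Take 20% cumulative loss over 5 years. The known-values percentage is about 29% whatever happens after loss, because later deaths are not seen. If the death hazard after loss is 6 times higher, true mortality is about 28%, so the two nearly agree. At 15 times higher it is about 32%, and the percentage understates.

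The same in counts: 20 subjects, 5 known deaths, 4 lost.
- Known-values percentage: 5/16 = 31.25%.
- None of the lost died: 5/20 = 25%. All died: 9/20 = 45%.
- Break-even: (5 + x)/20 = 5/16 gives x = 1.25, so two deaths among the four turn overstatement into understatement.

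**3. Reports during accrual, 2 years**

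Assume uniform accrual over 5 years, a report at year 5 and no loss. Then 3/5 of subjects have reached 2 years. S(2) = 0.80·(0.75/0.80)^0.25 = 0.787, so true mortality is 21.3%. Among the 2/5 not yet at 2 years, the average proportion already dead is 18.4%.
- Deaths counted: 0.6·0.213 + 0.4·0.184 = 0.201.
- Known alive at 2 years: 0.6·0.787 = 0.472.
- Percentage: 0.201/(0.201 + 0.472) = 29.9%.

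Limiting the denominator to subjects whose 2-year date has passed gives 21.3%. By year 10, the planned end, every 5-year date has passed and without loss the 5-year figure is 25.0%.

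**4. Interval**

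For 0 events in 20 the two-sided exact 95% upper limit is 1 − 0.025^(1/20) = 16.8%. The plan would report 0% alone.

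**5. The formal test**

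At n = 20, one death gives a one-sided upper limit of 21.6% and two give 28.3%, so at most one death meets the 25% rule. Nothing above changes this.

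**The case against.** Several points on the other side are sound.

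- **A reader might infer that late mortality is necessarily overstated because every death becomes known.** The documents do not say so. Three contact attempts can miss a death after loss, and step 2 shows that the direction can reverse.
- **A reader might infer that survivors not yet due distort the final result.** They do not: follow-up runs 5 years past the last enrolment. The effect is confined to reports during accrual, and arises only if those reports tabulate late rates, count early deaths and omit equally recent survivors. The plan does not specify that rule.
- **The denominator is implied, not stated.** Showing the number of known values also tells readers how much is missing.
- **For the non-fatal events no bias is demonstrated.** With complete follow-up, the simple proportion equals the cumulative incidence with death competing. It goes wrong only if event-free deaths are treated as unknown, and the plan is silent.
- **Kaplan-Meier is not a full cure.** It too assumes loss unrelated to prognosis. Subjects without an implant plausibly fare worse: section 2.1.1 cites 50% one-month survival without surgery.
- **The size is modest.** A 4-point shift compares with a standard error of √(0.25·0.75/20) = 9.7 points. Section 3.3.4.10 has implanted subjects who discontinue contacted for a final assessment, which may recover some vital status.
- **A reader might infer that a bare 0/20 would pass as no stroke risk.** That is speculative: the protocol names stroke as a risk in several places.

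These points limit what can be claimed about direction and size. They leave a method for most of the primary endpoint with no stated denominator, censoring rule or interval, in a study whose own rules truncate follow-up.

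**Conclusion.** The concern holds in limited form and should be acted on. Two things are certain from the text: the late primary endpoints have no censoring, competing-risk or interval method, and follow-up is incomplete for some subjects.

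The size is conditional. If known values are the denominator and loss is unrelated to prognosis, 5-year mortality of 25% is reported as about 29% or 34% at 5% or 10% loss per year. Both loss rates are assumptions, and the survival curve is borrowed from a cited series. With loss concentrated in sicker subjects the figure can be too low. The 30% against 21% at 2 years applies to reports during accrual under one reading of the denominator. For stroke, re-intervention and conversion neither direction nor size can be given.

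The 30-day test stands as written. The affected summaries are descriptive in an early feasibility study, so the consequence is misleading late rates rather than a wrong formal decision.

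**What to change.** In section 3.3.5.3:

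1. Report death by Kaplan-Meier at 1, 2 and 5 years, with numbers at risk and 95% confidence intervals.
2. Report stroke, re-intervention and conversion by cumulative incidence (Aalen-Johansen), with death as a competing event.
3. Time events from the procedure date and censor at last contact. Apply the same rule in reports made during accrual.
4. Give exact 95% confidence intervals for the 30-day proportions, and keep the exact 30-day test.
5. Add best- and worst-case bounds for subjects of unknown status, in particular in the ITT set, where Kaplan-Meier alone is not enough.

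Separately, reconcile the follow-up statements for unimplanted, aborted, observed and converted subjects in sections 3.3.4.1, 3.3.4.8 and 3.3.4.9, so that it is clear whose late status is meant to be known.

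The cost is analysis-plan wording, a little more analysis with standard software, and no new visits. The method needs event dates and last-contact dates. The case report forms are not in the text reviewed, so the sponsor should confirm that both are captured. Intervals at n = 20 will be wide, which reflects what the study can show.
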